practical part (i.e., microteaching) has been previously identified as essential for applying what has been learned in contexts as close to reality as possible (Aelterman et al., 2013). Ultimately, the adoption of a congruent style, where trainers implement the program using (de)motivating teaching styles has also been positively perceived by PE teachers. This approach allows them to observe real-life examples of how to implement these strategies effectively (Aelterman et al., 2013). Moreover, in line with SDT, it could lead to an immediate effect on the teachers' need satisfaction during the training that has been positively associated with effectiveness and feasibility beliefs in terms of autonomy support and structure, as well as teachers' intentions to apply the proposed strategies (Aelterman et al., 2016).

Finally, while previous studies have considered gender as a covariate to analyze the effects of SDT-based interventions, gender differences in study variables are seldom reported for both teachers and students. Given prior SDT-related research indicating that (de)motivating teaching behaviours may be perceived differently by boys and girls students (White et al., 2021) and male and female teachers (García-Cazorla et al., 2024), it is crucial to determine whether the intervention is equally effective for both genders to mitigate any potential gender-related inequities.

To extend previous knowledge, this mixed-method study describes the protocol of a motivational training program, based on the circumplex model, aimed at improving (de)motivating teaching styles/approaches among PE teachers. The first hypothesis suggests that the features of the motivational training program will be positively perceived by PE teachers (H1). We also hypothesize that experimental school female and male teachers will perceive improvements in several antecedents, autonomy and competence satisfaction/frustration at work, (de)motivating teaching styles/approaches, and (mal)adaptive outcomes at least at the end of the intervention implementation toward students (H2). Finally,

both boys and girls from experimental groups will perceive improvements in their PE teachers' (de)motivating teaching styles/approaches, autonomy and competence satisfaction/frustration in PE, and adaptive outcomes in PE lessons (H3).

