### **Sample size calculation**

The sample size for this intervention-based study was calculated using R Studio to ensure adequate power in the detection of potential statistically significant effects.

Considering a multi-level design nesting center, PE teacher and group, the sample size calculation was grounded on an anticipated effect size of 0.5, reflecting a moderate impact of the intervention. The power of the study was set at 80% with a significance level (alpha) of 0.05, aligning with common practices in educational research (McConnell et al., 2019).

Acknowledging the inherent structure of this study, an Intra-Class Correlation (ICC) of 0.1 was assumed based on similar educational settings (Hedges & Hedberg, 2007). This ICC estimate accounted for the expected homogeneity within the three levels (class group within PE teacher, PE teacher within center). To accommodate potential participant dropout, particularly among students, we incorporated a 40% anticipated dropout rate into our calculations (e.g., Meerits et al., 2022). The minimum sample size was adjusted to 210 students across 15 PE teachers, averaging 14 students per teacher. This adjustment ensures that our study maintains sufficient statistical power even in the face of anticipated losses, thereby safeguarding the integrity and validity of our findings.

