## ***Measures***

### ***Questionnaires***

The following PE teachers' variables will be measured using Google Forms before the training program (T1), as well as during (T2) and at the end of the implementation of the intervention with their students (T3) (see Figure 1):

**Socio-demographic variables.** Age, gender, teaching experience, type of school (public or private), and school location (rural or urban) will be self-reported by teachers.

**(De)motivating teaching styles and approaches towards students.** To assess self-reported (de)motivating teaching styles toward students, the Spanish version of the SIS in Physical Education (SIS-PE; (Burgueño, Abós, et al., 2024) will be used. The SIS-PE comprises 12 typical teaching situations consisting of four items each (i.e., 48 items). Autonomy-supportive items are categorised into participative (four items) and attuning (eight

items) approaches. Structure items are operationalised into guiding (seven items) and clarifying (five items) approaches. Control items are divided into demanding (seven items) and domineering (five items) approaches. Chaos items are operationalised into abandoning (eight items) and awaiting (four items) approaches. For instance, this situation “At the start of class...” is followed by four items: you can explore students’ prior knowledge of the topic (attuning), set up a class clearly and straightforwardly (clarifying), demand application of what’s taught (demanding), or just begin and let the class evolve (awaiting)”. It should be noted that, since teachers’ perceptions of their (de)motivating teaching styles could be different according to the classroom group, teachers will have to answer the questionnaire taking into account the groups of students selected for the study. Teachers’ responses will be assessed using a 7-point Likert scale ranging from 1 (“Does not describe me at all”) to 7 (“Describes me perfectly”).

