### ***Analysis plan***

#### ***Quantitative analyses***

Firstly, the effects of the four sessions of the training program on the study variables assessed in teachers will be examined. The overall mean for each of the 11 variables perceived by PE teachers about the quality of the training program (e.g., interaction, innovation, interest, intelligibility, etc.) will also be calculated, representing the mean across the different sessions. A repeated measures analyses of variance (ANOVA) will be used to assess PE teachers' global appreciation of 11 variables related to the quality of the training program (e.g., interaction, innovation, interest, intelligibility, etc.) across the sessions of the training (i.e. within-subject analyses). Accordingly, each of the training sessions will be introduced as an independent variable (i.e. within-subject factor) and repeated measures of the PE teachers-related variables will be entered sequentially as dependent variables.

Secondly, the effects of the intervention implementation in PE lessons on study variables for both teachers and students will also be examined. Levene and Kolmogorov–Smirnov tests will be used to ensure the equality of variances and normal data distribution, respectively ( $p > .05$ ). Cronbach's coefficient will be calculated for each study variable across the three measurements. To examine the effects of the intervention on study variables, a  $3 \times 2$  (time x condition) repeated measures multivariate analysis of covariance (MANCOVA) will be performed for both teachers and students. Age, gender, teaching experience, type of school (public or private), and school location (rural or urban) will be introduced as covariates among teachers, while age, gender, and school grade level will be introduced as covariates among students. Subsequently, to examine intragender differences of the intervention on study variables, a  $3 \times 2 \times 2$  (time x condition x gender) repeated measures MANCOVA will be performed for both teachers and students. The same covariates will be entered as previously analysis, excluding gender. Multiple paired t-tests with Bonferroni correction will be calculated to determine between-group (i.e., experimental-control group) and within-group (i.e., pre-post) differences. Cohen's criteria will be used as indicators of small (.01), moderate

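### The effect test treats T1 as an outcome wave and pools T2 with T3, so it uses the baseline less efficiently than adjustment would and does not isolate the end-of-intervention difference in H2

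*Protocol*

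**What the plan says.** All statements are in the protocol.

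- **Effect test** (Quantitative analyses): for intervention effects, a 3 × 2 (time × condition) "repeated measures multivariate analysis of covariance (MANCOVA) will be performed for both teachers and students". Time has three levels, so T1 is one of the outcomes.
- **Covariates** (same section): five are listed for the teacher model: "Age, gender, teaching experience, type of school (public or private), and school location (rural or urban) will be introduced as covariates among teachers". The student model has a shorter list of three: "age, gender, and school grade level will be introduced as covariates among students". The T1 score is in neither list.
- **Follow-up tests** (same section): "Multiple paired t-tests with Bonferroni correction will be calculated to determine between-group (i.e., experimental-control group) and within-group (i.e., pre-post) differences".
- **Timing** (Questionnaires): teachers are measured "before the training program (T1), as well as during (T2) and at the end of the implementation", and students likewise. T1 is therefore a true pre-intervention baseline.
- **Hypothesis** (end of the Introduction): for teachers, H2 expects improvement in antecedents, needs, teaching styles and "mal)adaptive outcomes at least at the end of the intervention implementation toward students (H2". H3, for students, names no time point.
- **Aim over time** (Discussion, fifth of the ten listed contributions): the intermediate measure is there to show how the variables change during the programme.

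**The concern.** A randomised trial with a pre-intervention score can use that score in two ways. It can be a covariate, which removes the part of the final score it predicts, or it can be another outcome wave. In the second case the T3 part of the interaction is a simple change from T1, which carries the noise of T1 in full. The protocol fixes the second way for teachers and students alike.

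The interaction also has 2 df per outcome. It is sensitive to any difference in profile, including one at T2 that has gone by T3. A significant result could then be read as support for H2 without an end-of-intervention effect.

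Precision is scarce here: the protocol plans at least 16 teachers and caps the number at 20, so it cannot be bought back by recruiting more.

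**Working it through.** **1. The plan's own figure.** The inputs, from Sample size calculation, are an "anticipated effect size of 0.5", 80% power, alpha 0.05 and 40% dropout. A two-sided comparison of two means at one time point needs 2 × (1.960 + 0.842)² / 0.5² = 62.8, so 63 per arm and 126 in all. Then 126 / 0.6 = 210, the stated number of students. This reproduces only if the ICC of 0.1 is not applied, which is a separate matter. What counts here is that the arithmetic is for a comparison at one time point, not for the 2-df test in the analysis section.

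**2. Variance of the T3 arm contrast.** Let r be the T1–T3 correlation, with equal variances, and express each variance relative to T3 alone. The protocol gives no r, so a range is assumed.

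- Change from T1: 2(1 − r)
- T3 adjusted for T1: 1 − r²
- Ratio, adjusted to change: (1 − r²) / [2(1 − r)] = (1 + r)/2

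| r | change | adjusted | ratio |
|---|---|---|---|
| 0.3 | 1.40 | 0.91 | 0.65 |
| 0.5 | 1.00 | 0.75 | 0.75 |
| 0.7 | 0.60 | 0.51 | 0.85 |

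This is the large-sample result. In simulation of 16 teacher means, where estimating the T1 slope has a cost, the ratio is about 0.8 to 0.9.

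**3. Power, student outcomes.** Students were averaged per teacher so that clustering is respected: 8 v 8 teachers, 28 × 0.6 = 16.8 students each, ICC 0.1, effect 0.5 at T3. The effect at T2 (0.25) and the correlations over time are assumptions. Each test is at two-sided 5%.

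| Correlation over time, student / teacher level | 2-df time × condition | change T3 − T1 | T3 adjusted for T1 | gain over 2-df test |
|---|---|---|---|---|
| 0.5 / 0.5 | 53% | 67% | 75% | 22 points |
| 0.3 / 0.5 | 44% | 60% | 70% | 26 points |
| 0.5 / 0.8 | 74% | 85% | 89% | 15 points |

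Repeat runs differ by up to about three points. If the full effect is already present at T2, the gain over the 2-df test falls to about 3 to 12 points.

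**4. Effect at T2 only.** With 0.5 at T2 and none at T3, the 2-df test was significant in 58% to 85% of runs. The T1-adjusted T3 comparison was significant in 5% (correlations 0.5 / 0.5), its nominal rate.

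**5. Teachers' own outcomes (H2).** There are 16 teachers and five covariates, so residual df are 16 − 2 − 5 = 9, or 8 once T1 is added. The (1 + r)/2 formula ignores this cost. Simulated variance ratios, adjusted to change:

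| r | first run | second run |
|---|---|---|
| 0.3 | 0.75 | 0.73 |
| 0.5 | 0.85 | 0.88 |
| 0.7 | 0.98 | 0.96 |
| 0.9 | 1.09 | 1.08 |

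Power at effect 0.5, with half of it at T2 (2-df test / change / adjusted), was 9/12/14% at r = 0.5, 11/16/16% at r = 0.7 and 25/36/34% at r = 0.9.

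**6. The follow-up tests.** A paired t-test suits the pre–post comparison within an arm. It cannot compare two independent arms. The sentence names no T3 contrast and no T1 adjustment. The longitudinal structural equation model is for predictive relationships among the variables, not for the arm effect.

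**The case against.** Several points on the other side stand.

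- **Validity.** Under randomisation the interaction contrast is unbiased and does use T1. A reader might infer that the test is invalid or that T1 is thrown away. Neither is so: T1 is used, but less efficiently.
- **The omnibus test is not the last step.** Between-group follow-up tests are planned, so a reader should not conclude that no comparison at T3 is intended. As worded, though, those tests cannot make that comparison.
- **Benefit for every analysis.** A reader might infer from the student figures that adjusting for T1 never loses. That does not carry to the teachers. With effect 1.0, r = 0.9 and the full effect at T2, power was 86% for the 2-df test, 88% for the change score and 85% with adjustment.
- **Hypothesis and evidence.** H2 concerns teachers, while the large power gains are for students, where H3 names no time point. The targeting argument therefore belongs to H2 and the efficiency argument mainly to H3.
- **Pattern over time.** This is a declared aim, and H2's wording does not exclude T2, so the time × condition test should stay.
- **Condition main effect.** It averages in the untreated T1 wave, and one could criticise it for dilution. But the protocol never names it as the effect test, so that criticism does not apply.

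The simulated powers are also for single outcomes, and those in the student table are without covariates. They are not the power of the full multivariate model.

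**Conclusion.** The point holds as a matter of efficiency and targeting, not of bias. The protocol itself fixes the test and both covariate lists, so this is not a detail left to a later plan.

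For students, adjusting T3 for T1 is more precise than the change score at any r below 1 in large samples, and it had more power than the 2-df test in the scenarios tried. The size depends on correlations and a T2 effect that the protocol does not give.

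For teachers' own outcomes the precision gain is modest at low r, about nil near r = 0.7 and slightly negative near r = 0.9. The case for change there is that H2 is a statement about T3 and the interaction does not isolate T3. The change should be made, but the planned analysis is not unsound without it.

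**What to change.** In Quantitative analyses, name as the effect test for each outcome the between-arm difference at T3, and separately at T2, adjusted for that outcome's T1 value and reported with its 95% confidence interval. Do this for students and teachers. It replaces the between-group part of the paired t-tests; the within-group pre–post comparisons can stay as description. Keep the time × condition test as a secondary analysis of the pattern over time, in line with the aim in the Discussion.

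The cost is wording only, with no new data. The T1 covariate takes one error df, which matters only in the teacher analysis. If the Bonferroni correction is spread over T2 and T3, part of the power gain shown is given back. The text should therefore say which contrasts the correction covers.

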interventions, it is crucial for researchers to understand the effectiveness of motivational training programs, not only in terms of the four (de)motivating teaching styles but also across the eight specific teaching approaches. Yet, no existing motivational training programs have incorporated this new circumplex approach. This mixed-method study sets out to expand existing knowledge by describing a protocol for a motivational training program based on the circumplex model, aimed at enhancing (de)motivating teaching styles, as well as (mal)adaptive outcomes among PE teachers and their students.

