### ***Participants and recruitment***

At least 16 secondary PE teachers, eight in the experimental group and eight in the control group, along with their respective students, will be expected to participate in this study. The maximum number of participating teachers will be capped at 20, due to the limited human resources of the research team. PE teachers will select at least two classroom groups comprising at least 14 students each to invite to participate in this study. Eligible students will be those aged 12 to 17 years in secondary schools. Participation will be voluntary and anonymous.

Various social media platforms (i.e., Instagram, Twitter, and WhatsApp) and other communication methods (i.e., email) will be used for teachers' recruitment. An informative poster will be launched, detailing the target sample, content, aims, and training program dates. This poster will also include two links (QR code): one with a document providing further information and another to registration through a brief Google Forms questionnaire. Regarding the additional information document, it is important to note that it will detail a more comprehensive overview of the objectives, the different phases of the program, inclusion criteria, the requirements that each teacher must accept to participate, and the

teaching skills that will be developed during the training program. Teachers with further inquiries can contact the research team via email or phone. The registration period will last approximately 21 days.

Once the interested PE teachers have registered, various inclusion criteria will be considered for the final selection: 1) Being an in-service PE secondary school teacher for the entire academic year; 2) Attending 100% of the training program sessions; 3) Fill in a short questionnaire at the end of each session of the training program, as well as fulfilling questionnaires of the study variables three times; 4) Allowing the recording of two PE lessons; 5) Participating in two focus groups, one at the end of the training program and one at the end of the study, and 6) Not participating in other training sessions related to PE instruction during the program. Moreover, the inclusion criteria for students will be: 1) Authorization from parents or legal guardians; 2) Completion of questionnaires of the study variables three times; 3) Regular participation in PE lessons.

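### The teacher MANCOVAs fix five (3×2) or four (3×2×2) covariates on 16 to 20 teachers; this leaves 8 to 13 error degrees of freedom and low power even for small outcome groups

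*Protocol*

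**What the plan says.** The number of teachers is bounded on both sides (Protocol, Participants and recruitment): "At least 16 secondary PE teachers, eight in the experimental group and eight in the control group", and "The maximum number of participating teachers will be capped at 20".

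Under Quantitative analyses, the main model is a 3×2 ("time x condition) repeated measures multivariate analysis of covariance (MANCOVA) will be performed for both teachers and students"). The teacher covariates are named: "Age, gender, teaching experience, type of school (public or private), and school location (rural or urban) will be introduced as covariates among teachers". A gender model follows, a 3×2×2 ("time x condition x gender) repeated measures MANCOVA will be performed for both teachers and students"), with the same covariates except gender. Follow-up comparisons are then described: "Multiple paired t-tests with Bonferroni correction will be calculated to determine between-group" as well as within-group differences.

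The questionnaire section defines 15 teacher outcomes at T1, T2 and T3: eight teaching approaches, four need scales, job satisfaction, emotional exhaustion and job performance. The text does not say how many of them enter one MANCOVA. The Introduction wants the programme's effects understood "not only in terms of the four (de)motivating teaching styles but also across the eight specific teaching approaches".

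The only computed sample size is for students: "The minimum sample size was adjusted to 210 students across 15 PE teachers". No power is given for any teacher-level test.

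**The concern.** Five covariates are a heavy load for 16 to 20 independent units. In a doubly multivariate repeated measures model, each outcome also uses two time contrasts, so the error degrees of freedom are spent twice: once on covariates and once on contrasts. What remains may be too little to detect even a large effect on teachers.

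The quantitative test of the second hypothesis (improvements perceived by experimental teachers) runs through these models. If the test has little power, a non-significant teacher result carries little information but could be read as evidence of no effect. The degrees of freedom are known before any outcome is seen, so the matter can be settled in advance.

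The t-test wording is a separate matter. Teachers in the experimental and control arms are different people, so a paired test does not apply to that contrast.

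**Working it through.** **The plan's own figure.** An effect of 0.5, 80% power and two-sided 5% (sidedness assumed) give 2 × (1.96 + 0.84)² / 0.5² ≈ 63 per arm, or 126. With 40% dropout, 126 / 0.6 = 210, and 210 / 14 = 15 teachers. The figure reproduces as a count of students (with no inflation for the stated ICC, which is outside this point). It does not address teacher-level tests.

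**Error degrees of freedom**, v = N − number of between-teacher parameters, with each two-level covariate using one:

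| Model | Parameters | v at 16 | v at 20 |
|---|---|---|---|
| 3×2, five covariates | 1 + 1 + 5 = 7 | 9 | 13 |
| 3×2×2, four covariates | 1 + 3 + 4 = 8 | 8 | 12 |
| 3×2, no covariates | 1 + 1 = 2 | 14 | 18 |

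**Form of the test.** Three times give two contrasts per outcome. For p outcomes, the time by condition test is F(2p, v − 2p + 1) and needs 2p ≤ v.

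- Two outcomes, 3×2: F(4,6) at 16 teachers and F(4,10) at 20. For the 3×2×2: F(4,5) and F(4,9). For the 3×2 without covariates: F(4,11) and F(4,15).
- Four outcomes at 16 teachers: F(8,2), 5% critical value 19.4, in the 3×2; F(8,1), critical value 238.9, in the 3×2×2.
- Eight approaches need 16 and all 15 outcomes need 30. Both exceed 13, so with the planned covariates a single joint model is singular at every permitted size.

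**Power for two outcomes in the 3×2.** The noncentrality is S × D. S is the sum of squares of the condition indicator left after the covariates: N/4 without them, and on average N/4 × (N − 6)/(N − 1) with five random ones. D is the squared standardised distance of the contrast means. Assumptions, none from the Protocol: effect d = 0.8 at T3 and d/2 to d at T2; equal correlation over time 0.4 to 0.7; between-outcome correlation 0 to 0.5; normal outcomes with demotivating scales reversed; covariates unrelated to outcomes, with age and experience correlated 0.7.

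The two extreme corners without covariates:

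- Least favourable (0.4 over time, 0.5 between outcomes, d/2 at T2), 16 teachers: D = (0.96/1.8) × (2/1.5) = 0.71; noncentrality 4 × 0.71 = 2.8; power 17%.
- Most favourable (0.7 over time, 0 between outcomes, d at T2), 20 teachers: D = (1.28/0.9) × 2 = 2.84; noncentrality 5 × 2.84 = 14.2; power 74%.

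| Two outcomes, d = 0.8 | 16 teachers | 20 teachers |
|---|---|---|
| Five covariates | 10-30% | 15-52% |
| No covariates | 17-58% | 22-74% |

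If the covariates happen to be balanced across arms, with correlation over time 0.5 to 0.7, the planned model gives 15-44% and 23-66%. At an effect of 0.5 under that assumption it gives 9-19% and 11-29%.

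**Per-outcome ANCOVA of T3 on condition and T1**, d = 0.8, correlation over time 0.4 to 0.7, no demographic covariates. After Bonferroni over eight approaches, power is 10-19% at 16 teachers and 15-29% at 20; at unadjusted 5% it is 34-52% and 43-63%. At d = 0.5 the corrected figures are 4-6% and 5-9%. The median 95% CI half-width is 0.78-1.00 SD and 0.68-0.87 SD. With the five covariates it is 1.03-1.32 SD and 0.82-1.06 SD, which is 33% and 21% wider.

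**If the covariates do predict the outcome.** In the same corrected ANCOVA, suppose they explain 40% of residual variance. Power with them at 20 teachers is 17-32%, against 15-29% without; at 16 it is 9-17%, against 10-19%. At 20% explained they still lose at both sizes; at 60% they win at both.

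**The case against.** **Singularity.** A reader might infer that the teacher analysis cannot be computed. The Protocol does not support that. It fixes neither the outcome grouping nor the multivariate test to be read, and grouping is commonly left to a statistical analysis plan. Two outcomes, such as the two approaches of one style, can be tested at every permitted size. The averaged within-subject test has 16 to 26 error degrees of freedom and is not singular even for 15 outcomes. It does need multivariate sphericity, which 16 to 20 teachers can hardly check. Nor are the covariates the sole cause: without them, 15 outcomes stay singular in the 3×2, and eight approaches are singular at 16 teachers and only F(16,3) at 20. Singularity is therefore a conditional warning.

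**Power.** The figures depend on assumptions, and the ranges are wide for that reason. No two-outcome combination tried reaches 80%.

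**Covariates.** Dropping them helps only if they are weakly prognostic. The Protocol gives no figure for this, so the gain is not guaranteed. This objection stands and limits the fix.

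**The second hypothesis.** The study is mixed-method, and the focus groups also cover needs, styles and job outcomes. They do not replace a between-arm comparison, but a reader should not conclude that the hypothesis is wholly untestable.

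**Gain from the remedy.** It is modest and also rests on assumptions. With between-outcome correlation 0.5 and half the effect at T2, power Bonferroni-corrected over the eight approaches is 3-5% / 5-11% (16 / 20 teachers) for four two-approach MANCOVAs with covariates, 6-12% / 8-20% without, and 10-19% / 15-29% for eight ANCOVAs. A full effect already at T2 raises the MANCOVA noncentrality by a third (1.28/0.96) and narrows that advantage.

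**Conclusion.** The point holds in a limited form. What the Protocol fixes is five or four covariates on 16 to 20 teachers, which leaves 9 to 13 or 8 to 12 error degrees of freedom. In the 3×2 the covariates take 5 of the 14 to 18 otherwise available. Even for two outcomes and an assumed large effect, the planned doubly multivariate test falls short of usual power, under the assumptions listed in the working. Near-saturation and singularity arise only under groupings that the text leaves open.

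The paired test for the between-arm contrast is an error regardless of grouping.

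This should be fixed before outcomes are seen. The degrees of freedom are certain; the power figures are conditional. The student models are not part of this point.

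**What to change.** For teachers only, replace both MANCOVAs and the between-group paired t-tests in Quantitative analyses with text to this effect:

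> For each teacher outcome, the T3 score is analysed by ANCOVA on condition, adjusted for that outcome's T1 score; the adjusted difference and its 95% CI are reported. T2 is analysed in the same way as secondary. Holm correction is applied to the T3 tests within pre-stated families. Condition by gender is reported as an exploratory estimate with a 95% CI.

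In addition:

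- Leave the five demographic covariates out of this main model, or keep at most one named in advance as prognostic. Show the fuller adjustment only as a sensitivity analysis.
- List the families (approaches or styles, need scales, job outcomes). Styles are built from the same items as the approaches, so name one of the two as the main family.
- State that the sample size section gives no teacher-level power and that a null teacher result will be inconclusive.

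The cost is analysis wording only; design, data and sample size are unchanged. The losses are the omnibus test, error control across families and some demographic adjustment. The last costs precision if the covariates explain roughly 40% or more of residual variance at 20 teachers, somewhat more at 16. The gender part of the second hypothesis becomes exploratory for teachers. The ANCOVA, like the planned models, treats teachers as independent, which should be checked if two come from one school.
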